6.4.2.2. Migraine-Specific Quality of Life

The transformed scores for the 3 domains (i.e., Role Function-Restrictive, Role Function-Preventive and Emotional Function) of MSQOL will be derived for baseline (visit 2), visit 3,

visit 4, and visit 5. The change from baseline values after the 3rd injection will be analyzed by ANCOVA method as described in Section 6.2.2 and MMRM method as described in Section 6.2.3.1.

6.4.2.3. EuroQol-5 Dimension Questionnaire

The number and percentage of patients rating their scale of 1 to 5 for the 5 domains will be presented before and after treatment. The change from baseline values on the visual analogue scale will be analyzed using the same ANCOVA method as described in Section 6.2.2 .

6.4.2.4. Patient Health Questionnaire

The change from baseline in total PHQ-9 score will be analyzed using the same ANCOVA method as described in Section 6.2.2 .

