- ^j Blood samples for plasma drug concentration determination will be collected prior to dosing at visits 2, 3, and 4.
- ^k Blood samples for serum ADA assessment will also be collected upon observation of any severe hypersensitivity reaction (eg, anaphylaxis).
- ^l A single blood sample for pharmacogenomic analysis will be collected at visit 2 or any visit thereafter from patients who consent to this procedure. A separate informed consent form for pharmacogenomic sampling must be signed by the patient.
- ^m Patients will respond first to the PHQ-2. They will respond to questions 3 through 9 (unique questions) of the PHQ-9 only if PHQ-2 is positive.
- ⁿ The eC-SSRS Baseline/Screening version will be completed at visit 2, and the eC-SSRS since Last Visit version will be completed at all other visits.
- ^o Injection sites will be assessed for erythema, induration, ecchymosis, and pain immediately and 1 hour after study drug administration. If a patient has severe injection site induration, erythema, and/or ecchymosis and/or grade 3 (severe) or grade 4 (worst possible) injection site pain at 1 hour after completion of study drug administration, the patient will be reassessed 3 hours after study drug administration and hourly thereafter until the reaction/pain is of moderate or less severity.

ADA=antidrug antibody; β -HCG=beta-human chorionic gonadotropin; ECG=electrocardiogram; eC-SSRS=electronic Columbia-Suicide Severity Rating Scale; EOT=end of treatment; EQ-5D-5L=EuroQol-5 Dimension, 5 response level version; FSH=follicle-stimulating hormone; HIT-6=6-item Headache Impact Test; MSQOL=Migraine-Specific Quality of Life; PGIC=Patient Global Impression of Change; PHQ-2=2-item Patient Health Questionnaire; PHQ-9=9-item Patient Health Questionnaire; V=visit; WPAI=Work Performance and Activity Impairment.

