- proportion of patients reaching at least 50% reduction and at least 75% reduction in the number of migraine days during the 4-week period after the 1st dose of study drug for whom this level of effect is sustained throughout the 12-week period after the 1st dose of study drug
- mean change from baseline (28-day run-in period) in the number of migraine days during the 12-week period after the 1st dose of study drug for patients not receiving concomitant preventive migraine medications
- mean change from baseline (28-day run-in period) in the number of migraine days during the 12-week period after the 1st dose of study drug for patients who used topiramate for migraine in the past
- mean change from baseline (28-day run-in period) in the number of migraine days during the 12-week period after the 1st dose of study drug for patients who used onabotulinumtoxinA for migraine in the past
- mean change from baseline (28-day run-in period) in the monthly average number of headache hours of any severity during the 12-week period after the 1st dose of study drug

- mean change from baseline (28-day run-in period) in the monthly average number of headache hours of at least moderate severity during the 12-week period after the 1st dose of study drug
- mean change from baseline (28-day run-in period) in the monthly average number of days of use of migraine-specific acute headache medications (triptans and ergot compounds) during the 12-week period after the 1st dose of study drug
- mean change from baseline (28-day run-in period) in the monthly average number of days with nausea or vomiting during the 12-week period after the 1st dose of the study
- mean change from baseline (28-day run-in period) in the monthly average number of days with photophobia and phonophobia during the 12-week period after the 1st dose of study drug
- mean change from baseline (day 0) in quality of life, as measured by the MSQOL questionnaire, at 4 weeks after administration of the last (3rd) dose of study drug
- mean change from baseline (day 0) in the health status, as measured by EQ-5D-5L questionnaire, at 4 weeks after administration of the last (3rd) dose of study drug
- mean change from baseline (day 0) in patient depression status, as measured by the PHQ-2 and the PHQ-9, at 4 weeks after administration of the last (3rd) dose of study drug

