3.3. Full Analysis Set

The full analysis set (FAS) will include all patients in the ITT population who receive at least 1 dose of study drug and have at least 10 days of post baseline efficacy assessments on the primary endpoint. The FAS will be used for all efficacy analysis.

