$$\frac{\sum \text{Days or hours of efficacy variable during the run – in period}}{\sum \text{Days with assessments recorded in the eDiary for the run – in period}} \times 28 \quad (3)$$

The *percentage of reduction* in the monthly average number of an efficacy variable will be calculated as

$$\frac{\text{baseline value} - \text{postbaseline value}}{\text{baseline value}} \times 100\% \quad (4)$$

where the baseline value is calculated by formula (3) and the postbaseline value in the equation is calculated by formula (1) for the variables *during the 12-week period* or by formula (2) for the variables *during the 4-week period* after each dose for months 1, 2 and 3.

The *baseline values* for calculating the change from baseline of the weekly number of days of the efficacy variables will use all data collected in the run-in period and be calculated as

$$\frac{\sum \text{Days of efficacy variable during the run-in period}}{\sum \text{Days with assessments recorded in the eDiary for the run-in period}} \times 7 \quad (5)$$

The *weekly number of days* of efficacy variables (e.g., days of headache with at least moderate severity, migraine days) for each week during the 4-week period after the 1st dose of study drug will be derived and normalized to 7 days equivalent using the following formula.

$$\frac{\sum \text{Days or hours of efficacy variable during the 7 days period}}{\sum \text{Days with assessments recorded in the eDiary for the 7 days period}} \times 7 \quad (6)$$

The FAS will be used for all efficacy analyses. Summaries will be presented by treatment group as randomized, unless otherwise noted. Descriptive statistics for all efficacy data will be presented by month (or week) and over 12-week period.

The primary and secondary endpoints analysis listed in Section 4.4 will be repeated for the per-protocol analysis set.

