6.4.1.4. Patient Health Questionnaire

The PHQ (Appendix G) is a 9-item questionnaire with each item corresponding to 1 criterion of the Diagnostic and Statistical Manual for Mental Disorders 4th edition diagnostic criteria for major depressive disorder. Each of the items is scored on a scale of 0 (“not at all”), 1 (“several days”), 2 (“more than half the days”), and 3 (“nearly every day”) based on the frequency of symptoms during the past 2 weeks (Spitzer et al 1999). The PHQ-2 was developed from the PHQ-9 to rapidly screen for depression and consisted of the first 2 questions of the PHQ-9. The PHQ-2 and the PHQ-9 are validated measures for detecting and monitoring depression, anxiety, and somatization (Kroenke et al 2010).

Patients will complete the PHQ-2 at baseline (visit 2) and the EOT visit (visit 5). If the PHQ-2 is positive (ie, a score of ≥ 3), patients will complete questions 3 through 9 (unique questions) of the PHQ-9.

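### The SAP models change in total PHQ-9 although items 3 to 9 are asked only when PHQ-2 is 3 or more; it also limits WPAI activity impairment to employed patients

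*SAP*

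**What the plan says.** **PHQ.** Section 2.2.3 lists as an exploratory endpoint the "mean change from baseline (day 0) in patient depression status, as measured by the PHQ-2 and the PHQ-9", 4 weeks after the third dose. The PHQ-2 is given at visit 2 and visit 5 (Section 6.4.1.4 and Table 1). The other seven items are conditional: "If the PHQ-2 is positive (ie, a score of ≥ 3), patients will complete questions 3 through 9 (unique questions) of the PHQ-9". Table 1 footnote m agrees: "They will respond to questions 3 through 9 (unique questions) of the PHQ-9 only if PHQ-2 is positive". Items score from 0 to 3. Section 6.4.2.4 then gives one sentence of analysis: "The change from baseline in total PHQ-9 score will be analyzed using the same ANCOVA method as described in Section 6.2.2". It names no subset and no scoring rule, and it does not analyse the PHQ-2. Section 3.3 says "The FAS will be used for all efficacy analysis", and Section 6.1 repeats this.

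**Item rules elsewhere.** Section 6.3.1.2 makes the HIT-6 total missing if any item is missing. Section 4.5 refers MSQOL items to the scoring instructions in Appendix E. No visible section gives a rule for the PHQ.

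**WPAI.** Section 6.4.2.5 applies the ANCOVA to all four WPAI scores in currently employed patients. Section 6.4.1.5 defines percent activity impairment as Q6/10. The WPAI endpoint in Section 2.2.3 carries no employment limit.

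**The concern.** A total PHQ-9 can be formed directly only at a visit where the PHQ-2 was positive, and a change score needs two such visits. The FAS is named as the analysis set, but the SAP does not settle who within it has a change score. There are two natural ways to follow the text:

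- **(a) Skipped items are missing.** Only patients positive at both visits enter the model. The missingness is built into the design and depends on a post-randomisation outcome, because a patient whose PHQ-2 falls below 3 by visit 5 is dropped. The arms are then compared among patients selected by their end-of-treatment status.
- **(b) Skipped items score 0.** Every patient with a PHQ-2 at both visits is kept, but the total jumps when the PHQ-2 crosses 3. The change score mixes change in symptoms with whether the items were asked.

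The two readings give different patients and different scores from the same data, and no visible text fixes the choice before unblinding. The one PHQ score that every patient is asked for at both visits, and that the endpoint names, is left without an analysis.

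The WPAI point is separate. Patients without a job are dropped from a score that applies to them. This costs scope and precision.

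**Working it through.** **1. Score bounds, from the SAP's own item scale (0 to 3) and cut-off (3).**

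- Visit with items asked: PHQ-2 of 3 to 6, plus seven items of 0 to 21, gives a total of 3 to 27. Under (a) every analysed total lies in this range at both visits, so no patient can be recorded as ending below 3.
- Visit with items skipped: PHQ-2 is 0 to 2. The true total could be anything from 0 to 2 + 21 = 23. Under (b) the recorded total is 0 to 2, an error of up to 7 × 3 = 21 points.
- Crossing the cut-off under (b): let PHQ-2 fall from 3 to 2 while items 3 to 9 keep the sum S. The true change is −1. The recorded change is 2 − (3 + S) = −(1 + S), which is −1 at S = 0, −8 at S = 7 and −22 at S = 21.

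**2. Base for an illustration.** Section 2.3 gives 289 evaluable patients per arm. Its inputs are a difference of 1.7, SD 6.29, two-sided alpha 0.05 and 90% power: n = 2 × (6.29/1.7)² × (1.960 + 1.282)² ≈ 287.7, so 288, against the stated 289. Power at 289 is 0.901, and 289/0.85 = 340. The plan's figure reproduces.

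**3. Patients left under (a), on assumed rates.** The SAP gives no PHQ-2 positivity rate. Assume that 5% to 30% are positive at baseline and that 30% to 70% of those are still positive at visit 5. Patients per arm = 289 × baseline share × share still positive. The half-width of the 95% confidence interval for an arm difference, in SD units, is t(0.975, 2n − 2) × √(2/n), for an unadjusted two-arm comparison.

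| Baseline positive | Still positive | Patients per arm | Share of 289 | 95% CI half-width |
|---|---|---|---|---|
| 5% | 30% | 4.3 (4) | 1.5% | 1.73 SD |
| 10% | 30% | 8.7 (9) | 3.0% | 1.00 SD |
| 30% | 70% | 60.7 (61) | 21% | 0.36 SD |
| all patients | n/a | 289 | 100% | 0.16 SD |

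**4. Direction of the distortion under (b).** In a simulated latent-severity model with about 7% to 27% positive at baseline and the treatment acting on items 1 and 2 only, zero-scoring enlarged the arm difference about 2 to 2.8 times. In a similar model with the treatment acting on all nine items, it shrank the difference to 0.59 to 0.82 times. The result depends on the scoring rule, but the direction of the error cannot be told in advance.

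**5. WPAI.** By the formulas in Section 6.4.1.5, time missed uses Q2 and Q4, impairment at work uses Q5, and overall work impairment uses Q2, Q4 and Q5. Activity impairment uses Q6 alone, so the employment condition is needed for the first three scores and not for the fourth.

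**The case against.** The strongest reply is that the PHQ rule may simply be unseen. Section 6.4.1.4 points to Appendix G, of which only the heading could be read. That stands as a limit on the claim that no rule exists. The contents list titles Appendix G as the questionnaire, however, and gives a separate scoring appendix only for the MSQ. A rule there would also not repair readings (a) and (b), and Section 6.4.2.4 would still leave the PHQ-2 unanalysed.

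Second, the patient counts rest on assumed rates and span a factor of about 14. The base of 289 completers is not the FAS, since early withdrawals also have visit 5 procedures. The half-widths ignore covariates (with the full three-arm model, n = 4 per arm gives about 1.96 SD, not 1.73). The SD among patients positive at both visits need not equal the SD in all patients. All of this is fair. The table shows the possible loss of data and is not an estimate, and the 21-point error is one patient's maximum. Only the score bounds come from the SAP itself.

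Third, the WPAI population is stated outright, so that analysis is specified. True, but it narrows an endpoint that has no such limit and excludes patients for whom Q6 is meaningful. The SAP also does not say at which visit employment is taken. If it were visit 5, the restriction would depend on a post-randomisation state.

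Finally, it can be said that one sentence fixing the PHQ-9 rule would be enough and that promoting the PHQ-2 is a preference. A fixed rule would remove the ambiguity, and it is offered below as the alternative. It would leave the selection under (a) or the jump under (b) in place.

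**Conclusion.** The concern holds and is minor. The planned PHQ-9 model does not fit the way the items are collected: one reading selects patients on their end-of-treatment outcome, and the other builds an artificial step into the score at the cut-off. The bounds (analysed totals of 3 to 27 under (a); recorded totals of 0 to 2 and an error of up to 21 points under (b)) follow from the SAP alone. The size and direction of the effect on the treatment comparison are unknown. Under the assumed rates, (a) would leave about 4 to 61 patients per arm. The WPAI restriction on activity impairment is unnecessary, and its size is also unknown because the SAP gives no employment rate. Both endpoints are exploratory and outside the Section 4.4 sequence, so primary and secondary conclusions are unaffected. Confidence is medium, mainly because the content of Appendix G was not available.

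**What to change.** - **Section 6.4.2.4:** make an ANCOVA of change in PHQ-2 score (0 to 6), in all FAS patients with data at both visits, the main exploratory PHQ comparison. Report the PHQ-9 total descriptively among those asked, with the proportion PHQ-2 positive at end of treatment by arm.
- **Alternative:** keep a PHQ-9 model as supportive, with the rule for skipped items and the included patients written down before unblinding.
- **Section 6.4.2.5:** keep the employment restriction for the three work scores only, say at which visit employment is taken, and analyse percent activity impairment (Q6/10) in all FAS patients with Q6 data.

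The cost is a few sentences in the SAP, and no new data are needed. The drawback is that the PHQ-2 is a narrower scale and the listed PHQ-9 endpoint becomes descriptive or supportive.

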6.4.2.5. Work Productivity and Activity Impairment Questionnaire : General Health V2.0

For the patients who are currently employed, their scores of

- percent work item missed due to health
- percent impairment while working due to health
- percent overall work impairment due to health
- percent activity impairment due to health

will be analyzed using the same ANCOVA method as described in Section 6.2.2.

6.4.2.6. Patient's Global Impression of Change Scale

The percentage of patients' dichotomous scale of " Yes" or "No" rated by PGIC assessments at 4-week after each dose will be analyzed by Cochran Mantel-Haenszel test stratified by baseline preventive migraine medication use (yes/no) as described in Section 6.3.2.

6.5. Subgroup Analysis

The ANCOVA analysis defined in Section 6.2.2 and MMRM analysis defined in Section 6.2.3.1 will also be applied to following subgroup populations analysis for the endpoints mean change from baseline in the monthly average number of headache days of at least moderate severity and number of migraine days.

- patients who are receiving or not receiving any concomitant preventive treatment
- patients who used topiramate for migraine in the past
- patients who used onabotulinumtoxinA for migraine in the past
- patients in different age group (18-45, >45 years old)
- patients in different race group (caucasian, non-caucasian)
- patients by sex

7. SAFETY ANALYSIS

7.1. General

The safety population will be used for all safety analyses. Summaries will be presented by treatment group and all TV48125 as actually received unless specified otherwise.

7.2. Study Drug Administration

Following the baseline assessments, eligible patients will be randomly assigned with stratification based on sex, country, and baseline use of preventive migraine medication (yes, no) to receive TEV-48125 at 675 mg followed by monthly TEV-48125 at 225 mg, TEV-48125 at 675 mg followed by monthly placebo, or monthly placebo.

Study drug will be administered by qualified study personnel as sc injections approximately every 28 days for a total of 3 doses, as follows:

- Patients randomized to receive TEV-48125 675/225/225 mg will receive 675 mg of TEV-48125 as 3 active injections (225 mg/1.5 mL) at visit 2 and 225 mg of TEV-48125 as 1 active injection (225 mg/1.5 mL) at visits 3 and 4.
- Patients randomized to receive TEV-48125 675 mg/placebo/placebo will receive 675 mg of TEV-48125 as 3 active injections (225 mg/1.5 mL) at visit 2 and placebo as a single 1.5-mL injection at visits 3 and 4.
- Patients randomized to receive TEV-48125 placebo will receive three 1.5-mL placebo injections at visit 2 and a single 1.5-mL placebo injection at visits 3 and 4.

Duration of treatment (days treated) is the number of days on treatment started from the 1st study drug administration day to the EOT visit day/early withdrawal day (EOT visit day – first day of study drug + 1). For subjects who are lost to follow-up, the EOT date is defined as the last study drug administration date +27.

Number (%) of patient receiving 1 dose, 2 doses, and 3 doses will be summarized using descriptive statistics by treatment group. Duration of treatment (days) will also be summarized using descriptive statistics for each treatment group.

7.3. Adverse Events

All adverse events will be coded using the MedDRA version 18.1.

For adverse event recording, the study period is defined for each patient as the time period from signature of the informed consent form through completion of visit 5 or the early withdrawal visit for patients who withdraw from the study for any reason.

Adverse events will be collected at each visit via adverse event inquiry.

The following are considered protocol-defined adverse events to be sent to the sponsor's Global Patient Safety and Pharmacovigilance Department for evaluation: ophthalmic adverse events of at least moderate severity, events of possible drug-induced liver injury (aspartate aminotransferase [AST] or alanine aminotransferase [ALT] $\geq 3 \times$ the upper limit of the normal

range [ULN], total bilirubin $\geq 2 \times$ the ULN or international normalized ratio [INR] >1.5), Hy's Law events, or events of suspected anaphylaxis and severe hypersensitivity reactions. Severe hypersensitivity reactions will be monitored using the diagnostic criteria for anaphylaxis as outlined by the 2006 Joint National Institute of Allergy and Infectious Disease/Food Allergy and Anaphylaxis Network Second Symposium on Anaphylaxis (Sampson et al 2006). In the event of suspected anaphylaxis, vital signs, including oxygen saturation and respiration rate, will be measured.

Summaries by treatment group will be presented for treatment emergent adverse events (overall and by severity), treatment emergent adverse events determined by the investigator to be treatment-related adverse events (overall and by severity), serious adverse events, protocol-defined adverse events, adverse events causing discontinuation from the study, non-serious treatment emergent adverse events and prior to treatment adverse events. Additionally the injection site reactions recorded as adverse events will be summarized by treatment group separately.

The incidence of adverse event will be summarized using descriptive statistics by SOC, PT, and severity of the adverse event. Each patient will be counted only once within a SOC or a PT by using the adverse events with the highest severity within each category. Treatment-related adverse event summaries will include adverse events related to study drug and adverse events with missing relationship to study drug. Adverse events with the missing flag indicating serious will be excluded from the summary of serious adverse events but included in the summary of non-serious adverse events.

Listings for deaths, serious adverse events, adverse events leading to discontinuation, injection site-related adverse events, and protocol defined adverse events will be presented. All information pertaining to adverse events noted during the study will be listed by subject, detailing verbatim given by the investigator, PT, SOC, date of onset, date of resolution, severity, and relationship to treatment. The onset of adverse events will also be shown relative (in number of days) to the 1st day of treatment. In addition, MedDRA dictionary terms for adverse event descriptions, and adverse event PTs by patient number and treatment group will be presented.

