Upon completion of the final study assessments, patients who complete all scheduled visits may be eligible to enter a long-term safety and efficacy study (Study TV48125-CNS-30051), consisting of a 12-month double-blind treatment period and a 6.5-month follow-up period. Patients receiving active study drug in the current study will continue receiving the same treatment (i.e., monthly sc TEV-48125 at 225 mg or quarterly sc TEV-48125 at 675 mg), and patients receiving placebo in the current study will be randomized in a 1:1 ratio to receive a loading dose of sc TEV-48125 at 675 mg followed by monthly sc TEV-48125 at 225 mg or quarterly sc TEV-48125 at 675 mg during the long-term safety and efficacy study. Patients who withdraw from the study before completing the 12-week evaluation period will have EOT visit (visit 5) procedures and assessments performed on the last day they receive the study drug or as soon as possible thereafter. Those patients who do not enter the long-term safety and efficacy study for any reason will be offered to enter the long-term safety extension for the purpose of evaluating ADA approximately 7.5 months (225 days [the approximate equivalent of 5 half-lives]) after administration of the last dose of study drug in this study.

The assessments and procedures performed during each study visit are detailed in [Table 1](#). The study schema is presented in [Figure 1](#).

The end of the study is defined as the date the last patient attends the EOT/early withdrawal visit (visit 5).

A total of 1020 patients are planned to be randomized in a 1:1:1 ratio (340 patients per treatment group) to receive sc TEV-48125 at 675 mg followed by 2 monthly sc doses of TEV-48125 at 225 mg, sc TEV-48125 at 675 mg followed by 2 monthly sc doses of placebo, or 3 monthly sc doses of matching placebo.

Figure 1: Overall Study Schema

PBO = placebo; V = visit.

Note: Baseline refers to the 28-day run-in period for headache variables and visit 2 (day 0) for all other variables.

Table 1: Study Procedures and Assessments

Study period	Pretreatment period (incl. screening visit and run-in period)	Double-blind treatment period			
		V1	V2	V3	V4
Month number	Month -1	Month 0	Month 1	Month 2	Month 3
Procedures and assessments (completed before dosing, when applicable, unless otherwise noted)	Screening days -28 to -1	Baseline dose 1 day 0 (+3 days)	Dose 2 day 28 (±3 days)	Dose 3 day 56 (±3 days)	EOT or early withdrawal day 84 (±3 days)
Informed consent	X				

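### SAP Section 7.3 counts adverse events of unknown seriousness as non-serious, the opposite direction to its neighbouring rule for unknown relationship

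*SAP*

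**What the plan says.** Section 7.3 of the SAP has two default rules for incomplete adverse event records, in adjacent sentences.

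- **Missing relationship to study drug.** "Treatment-related adverse event summaries will include adverse events related to study drug and adverse events with missing relationship to study drug". The unknown is resolved towards the drug being responsible.
- **Missing seriousness.** "Adverse events with the missing flag indicating serious will be excluded from the summary of serious adverse events", and the sentence continues "but included in the summary of non-serious adverse events". The unknown is resolved towards the event not being serious.

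The same section plans a summary of SAEs and a summary of non-serious treatment-emergent events, both by treatment group. It also plans a by-subject listing of all adverse events, "detailing verbatim given by the investigator, PT, SOC, date of onset, date of resolution, severity, and relationship to treatment". Seriousness is not among the items named. Separate listings are planned as well: "Listings for deaths, serious adverse events, adverse events leading to discontinuation, injection site-related adverse events, and protocol defined adverse events will be presented".

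**The concern.** A default for missing data should be judged by what it does when data are missing. Here it does more than hold back a doubtful event: it places an event of unknown seriousness in the non-serious table, as if seriousness had been assessed and ruled out.

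That is the less cautious direction for a safety table, and it departs from the approach one sentence earlier. Safety and tolerability are among the primary objectives (Section 1.1), and SAE tables often rest on small counts, so single events can matter. Because seriousness is not named for the full listing, the SAP also does not ensure that a reader of the study report could see which events had been classified by default.

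**Working it through.** The SAP has no figure to reproduce here. The check sets the rules side by side and then bounds the effect.

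**Step 1: direction of the two rules (Section 7.3)**

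| Field missing | Table the event enters | Direction |
|---|---|---|
| Relationship to study drug | Treatment-related | Cautious |
| Seriousness | Non-serious, and left out of SAEs | Not cautious |

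Both rules can be carried out as written, for the same event if need be. They differ in principle and do not contradict each other.

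**Step 2: effect on an arm's SAE incidence**

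For one arm, let

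- N = patients in the arm;
- S = patients with at least one event flagged as serious;
- M = patients with no flagged SAE but at least one event whose flag is missing;
- T = those of the M patients whose unflagged event was truly serious, so 0 ≤ T ≤ M.

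Then

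- incidence under the SAP rule = S/N;
- true incidence = (S + T)/N;
- incidence with missing counted as serious = (S + M)/N.

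Since S ≤ S + T ≤ S + M, the SAP rule gives the lower bound and the worst-case rule the upper bound. The SAP rule errs by −T/N and the worst-case rule by +(M − T)/N. If M = 0, all three agree.

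**Step 3: size**

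The SAP plans "340 patients per treatment group" (Section 2.1). Take N = 340. The safety population contains only treated patients, analysed as treated (Section 3.2), so the actual denominator may differ slightly. The SAP does not give the number of missing flags, so T is an assumption, shown over a range:

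| Assumed T in one arm | T/340 | Understatement, percentage points |
|---|---|---|
| 0 | 0/340 | 0 |
| 1 | 1/340 | 0.29 |
| 2 | 2/340 | 0.59 |
| 5 | 5/340 | 1.47 |

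A patient contributes to T only if three conditions hold together: the flag is still missing at lock, the event was truly serious, and the patient has no other SAE. The third condition applies to overall incidence. Within a system organ class or preferred term, where a patient is counted once, it means no other SAE in that same row.

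**Step 4: can the affected events be found?**

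They stay in the overall and by-severity summaries. They also appear in the separate listings if they led to death or discontinuation, were injection-site events, or were protocol-defined. An event outside those categories appears in the full listing, but seriousness is not named there. The promise to list all information about adverse events may be meant to cover it; the text does not secure it.

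**The case against.** The strongest reply has four parts.

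**There is no contradiction.** A reader might infer one from the adjacent sentences. The document does not support that: the rules govern different fields and both can be followed. What stands is a difference in direction with no stated reason.

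**The loss is conditional.** A reader might infer that every affected event removes one SAE from the count, or that a large share of an arm's SAEs is at risk. Neither follows. An unflagged event that was not serious is classified correctly by the present rule. As for the share, if 1–2% of 340 patients had an SAE (about 3 to 7 patients), one lost patient would be 1/7 = 14% to 1/3 = 33% of that count. But the 1–2% is an assumption: the SAP gives no SAE rate and no count of missing flags, so these percentages illustrate and do not establish a size.

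**Counting every unflagged event as serious can only overstate.** This is correct. If SAEs are uncommon, most unflagged events may not be serious, and forcing them into the SAE count without marking them would exchange one error for another. This objection shapes the fix: the worst-case count needs a separate row, so that both bounds are visible.

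**The events are not hidden, and flags may all be complete.** Total adverse event counts are unaffected, deaths also receive narratives (Section 7.5), and final analyses follow database lock (Section 2.5.2). Nothing in the SAP suggests that flags will be missing. The absence of a query step should not be held against it, since data cleaning is commonly described elsewhere. All of this limits the size of the point. It gives no reason for the direction of a rule that operates only when a flag is missing.

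**Conclusion.** The point holds as a narrow safety-reporting matter. Section 7.3 resolves missing seriousness in the less cautious direction, unlike its rule for missing relationship, and gives no reason.

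Measured against the truth, the rule can only understate an arm's SAE incidence or leave it unchanged. The ceiling is 0.29 percentage points per affected patient in an arm of 340, under the three conditions in the working; the effect is nil if all flags are complete. How many patients would be affected cannot be known from the SAP. Nor can the effect on the comparison between arms, which depends on how missing flags fall across them.

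Efficacy, multiplicity, sample size and total adverse event counts are not touched. The change is worth making because it is cheap and the default has no stated justification.

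**What to change.** Replace the sentence on missing seriousness in Section 7.3 with:

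*Adverse events whose seriousness is still missing at database lock will not be counted as non-serious; they will be included in the summary of serious adverse events as a worst case, shown in a separate row for missing seriousness, and flagged in the adverse event listing.*

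Also add seriousness to the items named for the by-subject listing of all adverse events.

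The cost is one replaced sentence, one added listing item and one table row that stays empty if all flags are complete. If a flag does remain missing, the worst-case SAE count may be slightly higher and may include events that were not serious. The separate row lets a reader see the count with and without them.
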